4.5.9.4 Consent to Participate in the Roche Clinical Repository

The Informed Consent Form will contain a separate section that addresses participation in the RCR. The investigator or authorized designee will explain to each patient the objectives, methods, and potential hazards of participation in the RCR. Patients will be told that they are free to refuse to participate and may withdraw their specimens at any time and for any reason during the storage period. A separate, specific signature will be required to document a patient's agreement to provide optional RCR specimens.

Patients who decline to participate will not provide a separate signature.

The investigator should document whether or not the patient has given consent to participate by completing the DNA Research Sample Informed Consent eCRF.

In the event of an RCR participant's death or loss of competence, the participant's specimens and data will continue to be used as part of the RCR research.

4.5.9.5 Withdrawal from the Roche Clinical Repository

Patients who give consent to provide RCR specimens have the right to withdraw their specimens from the RCR at any time for any reason. If a patient wishes to withdraw consent to the testing of his or her specimens, the investigator must inform the Medical Monitor in writing of the patient's wishes through use of the RCR Subject Withdrawal Form and, if the trial is ongoing, must enter the date of withdrawal on the DNA Research Sample Withdrawal of Informed Consent eCRF. The patient will be provided with instructions on how to withdraw consent after the trial is closed. A patient's withdrawal from Study ML29966 does not, by itself, constitute withdrawal of specimens from the RCR. Likewise, a patient's withdrawal from the RCR does not constitute withdrawal from Study ML29966.

4.5.9.6 Monitoring and Oversight

RCR specimens will be tracked in a manner consistent with Good Clinical Practice by a quality-controlled, auditible, and appropriately validated laboratory information

management system, to ensure compliance with data confidentiality as well as adherence to authorized use of specimens as specified in this protocol and in the Informed Consent Form. Roche monitors and auditors will have direct access to appropriate parts of records relating to patient participation in the RCR for the purposes of verifying the data provided to Roche. The site will permit monitoring, audits, IRB/EC review, and health authority inspections by providing direct access to source data and documents related to the RCR samples.

4.6 PATIENT, TREATMENT, STUDY, AND SITE DISCONTINUATION

4.6.1 Criteria for Re-Treatment with Ocrelizumab

Prior to re-treatment with ocrelizumab, patients will be evaluated for the following conditions and laboratory abnormalities. If any of these are present prior to re-dosing, further administration of ocrelizumab should be suspended until these are resolved or held indefinitely:

- *Life-threatening (Grade 4) infusion-related event that occurred during a previous ocrelizumab infusion*
- *Any significant or uncontrolled medical condition or treatment-emergent, clinically significant laboratory abnormality*
- *Active infection*
- *Ongoing pregnancy*

In addition to the criteria above, patients with PPMS will also be evaluated for:

- $\text{ANC} < 1.5 \times 10^3/\mu\text{L}$

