4.6.3 Study Treatment Discontinuation

Patients must discontinue study treatment if they experience any of the following:

- Ongoing pregnancy: Please note that the pregnancy should be followed up to determine outcome, including spontaneous or voluntary termination, details of birth, and the presence or absence of any birth defects, congenital abnormalities, or maternal and newborn complications.
- Life-threatening IRR or serious hypersensitivity reaction
- Active hepatitis B infection or reactivation
- PML
- Active tuberculosis, either new onset or reactivation

The primary reason for study treatment discontinuation should be documented on the appropriate eCRF. Patients who discontinue study treatment prematurely will not be replaced.

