5.1.2 Management of Patients Who Experience Specific Adverse Events

Guidelines for management of specific adverse events are outlined in [Table 4](#). Additional guidelines are provided in the subsections below.

Table 4 Guidelines for Management of Specific Adverse Events

Event	Action to Be Taken
Mild to moderate IRR	
• If the event that a patient experiences is a mild to moderate IRR (e.g. headache), the infusion rate should be reduced to half the rate at the time of the event.• This reduced rate should be maintained for at least 30 minutes. If tolerated, the infusion rate may then be increased according to the patient's initial infusion schedule.
Severe IRR (or complex of flushing, fever, and throat pain)	
• If a patient experiences a severe IRR or a complex of flushing, fever, and throat pain symptoms, the infusion should be interrupted immediately and the patient should receive symptomatic treatment.• The infusion should be restarted only after all symptoms have resolved.• The initial infusion rate at restart should be half of the infusion rate at the time of onset of the reaction.

Table 4 Guidelines for Management of Specific Adverse Events (cont.)

Life-threatening or disabling IRR (e.g., anaphylaxis)	
• Immediately stop ocrelizumab if there are signs of a life-threatening or disabling IRR during an infusion, such as acute hypersensitivity or acute respiratory distress syndrome.• The patient should receive appropriate treatment.• Permanently discontinue ocrelizumab in these patients.
---	--

IRR=infusion-related reaction.

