5.4.3 Reporting Requirements for Pregnancies

5.4.3.1 Pregnancies in Female Patients

Female patients of childbearing potential will be instructed to immediately inform the investigator if they become pregnant during the study or within 24 weeks after the last dose of study drug. A Clinical Trial Pregnancy Reporting Form should be completed and submitted to the Sponsor or its designee immediately (i.e., no more than 24 hours after learning of the pregnancy), either by faxing or by scanning and emailing the form using the fax number or email address provided to investigators. Pregnancy should not be

recorded on the Adverse Event eCRF. The investigator should discontinue study drug and counsel the patient, discussing the risks of the pregnancy and the possible effects on the fetus. Monitoring of the patient should continue until conclusion of the pregnancy. Any serious adverse events associated with the pregnancy (e.g., an event in the fetus, an event in the mother during or after the pregnancy, or a congenital anomaly/birth defect in the child) should be reported on the Adverse Event eCRF. In addition, the investigator will submit a Clinical Trial Pregnancy Reporting Form when updated information on the course and outcome of the pregnancy becomes available.

5.4.3.2 *Pregnancies in Female Partners of Male Patients*

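### Protocol 4.6.1 does not say whether ocrelizumab is suspended or stopped after a Grade 4 infusion event or in pregnancy, while 4.6.3, Table 4 (infusion reactions) and 5.4.3.1 (pregnancy) say to discontinue

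*Protocol*

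**What the plan says.** Four places in the Protocol bear on this.

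- **4.6.1, re-treatment criteria.** Four general conditions are listed, plus a neutrophil threshold for PPMS patients. Two of the four are "Life-threatening (Grade 4) infusion-related event that occurred during a previous ocrelizumab infusion" and "Ongoing pregnancy". One sentence governs the whole list: if any condition is present, "further administration of ocrelizumab should be suspended until these are resolved or held indefinitely".
- **4.6.3, treatment discontinuation.** The opening line is "Patients must discontinue study treatment if they experience any of the following". The list includes "Life-threatening IRR or serious hypersensitivity reaction" and "Ongoing pregnancy: Please note that the pregnancy should be followed up to determine outcome".
- **5.1.2, Table 4.** For a life-threatening or disabling infusion reaction: "Permanently discontinue ocrelizumab in these patients". The table does not deal with pregnancy.
- **5.4.3.1, pregnancy in female patients.** "The investigator should discontinue study drug and counsel the patient".

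Two pointers also matter. Footnote k in Appendices 1, 2 and 3, attached to the pre-dose safety laboratory row, refers the site to 4.6.1 when it judges eligibility. Section 4.3.2.1, in the text after Table 3, refers to 4.6.3 for discontinuation guidance.

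**The concern.** The pre-dose check is where a site decides whether to infuse. The section that governs it offers two courses, a pause that ends on resolution or an open-ended hold, and assigns neither to a condition. Other sections give a firmer instruction for two of the same conditions. An investigator working only from 4.6.1 could reasonably conclude that dosing may restart once the condition has passed. One who turns to 4.6.3 would conclude that treatment is over.

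This is first a question of patient safety wording. The secondary issue is how the event is recorded. SAP 4.2 tabulates reasons for stopping ocrelizumab and, at an interim analysis, counts a patient with no completed discontinuation form as still on treatment. SAP 2.2.5 lists adverse events leading to withdrawal of treatment as an outcome. An event treated as a pause and one treated as a stop would enter those tables differently.

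**Working it through.** No figure in the plan depends on this point, so the check is a comparison of the texts by condition, followed by a rough size.

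**Comparison**

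| Condition | 4.6.1 | 4.6.3 | Table 4 | 5.4.3.1 |
|---|---|---|---|---|
| Life-threatening infusion reaction | Pause until resolved, or hold indefinitely | Discontinuation mandatory | Discontinue permanently | Not covered |
| Ongoing pregnancy | Pause until resolved, or hold indefinitely | Discontinuation mandatory | Not covered | Discontinue study drug |

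1. *Do the triggers coincide?* For the reaction they are worded differently: Grade 4 in 4.6.1, life-threatening in 4.6.3, life-threatening or disabling in Table 4. A life-threatening Grade 4 infusion reaction falls under all three. For pregnancy, 4.6.1 and 4.6.3 name the same condition.
2. *Does 4.6.1 settle which option applies?* No. One sentence covers a mixed list in which some items clear up (an active infection) and one is a past event.
3. *How firm is each instruction?* 4.6.1 and 5.4.3.1 are phrased with should, and 4.6.3 with must. Only Table 4 says permanently, and only for the infusion reaction.
4. *Is there a bridge between the sections?* 4.6.1 does not cite 4.6.3, and neither does footnote k. The one pointer to 4.6.3 in the dosing text sits in 4.3.2.1, apart from the visit schedules.
5. *Is the overlap wider?* The remaining 4.6.1 conditions do not appear as such in 4.6.3. Active hepatitis B and active tuberculosis in 4.6.3 are special cases of active infection, and a specific-over-general reading can settle those.
6. *Is footnote m part of the conflict?* No. It says to withhold drug after a positive urine test until a serum test confirms pregnancy, which is a step before any rule for confirmed pregnancy applies.

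**Size**

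Protocol 1.2.1.1 reports one serious infusion reaction on ocrelizumab in the pooled RMS studies, of Grade 4. It reports 5 patients (1.0%) with a serious reaction on ocrelizumab in the PPMS study and gives no Grade 4 count there. Serious and Grade 4 are different scales (Protocol 5.2.2). If every Grade 4 reaction in that study was also classed as serious, which is an assumption, 1.0% is an upper bound for Grade 4. Expected PPMS patients are then at most:

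- 0.010 × 16 = 0.16 at the Protocol's planned number;
- 0.010 × 30 = 0.30 at the approximate number in SAP 2.3.

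For RMS, the summary of changes gives a serious-reaction rate of 0.1%, in text since removed. At that rate, 0.001 × 88 = 0.09 patients.

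These rates come from studies with longer controlled periods than the main period here, so they are orders of magnitude only. The documents give nothing from which to estimate pregnancies.

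**The case against.** The best defence is that the rules are cumulative. 4.6.1 says when not to dose. It does not say that a patient may resume in spite of another section. The mandatory wording of 4.6.3 comes two subsections later, 4.3.2.1 sends the reader there, and Table 4 and 5.4.3.1 repeat the stop. The option of an indefinite hold is compatible in effect with discontinuation. It is also the natural reading for a Grade 4 event at a previous infusion, since a past event does not resolve in the ordinary sense.

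Much of this stands. A careful reader of the whole Protocol would probably stop treatment. It does not remove the conflict, because 4.6.1 ties neither option to a condition. A reaction whose symptoms cleared the same day could be called resolved, and a pregnancy plainly ends. The schedules also send the site to the section without the mandatory rule.

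Three stronger readings are tempting and are not supported:

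- **That 4.6.1 authorises re-dosing.** It leaves that reading open, but it offers the indefinite hold in the same sentence.
- **That Table 4 requires permanent discontinuation in pregnancy.** Table 4 concerns infusion reactions. For pregnancy the relevant texts are 4.6.3 and 5.4.3.1, and neither says permanently.
- **That discontinuation counts will differ by site.** The ambiguity makes this possible, but nothing in the documents shows divergent practice.

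**Conclusion.** The point holds as an internal inconsistency in the Protocol. For a life-threatening infusion reaction and for ongoing pregnancy, 4.6.1 offers two courses without assigning either, while 4.6.3 requires discontinuation for both, Table 4 requires it permanently for the reaction, and 5.4.3.1 calls for it in pregnancy. The conflict is most explicit for the infusion reaction, because of Table 4. The reading that dosing may restart comes more easily for pregnancy.

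The number affected is likely to be small: on the rates above, fewer than one infusion-reaction case is expected in either cohort. A reader might take the PPMS 1.0% as the share of patients affected. It is not, because it counts serious reactions. The primary endpoints, which are changes in CSF biomarkers, do not turn on this wording. The case for acting rests on the possible consequence for an individual patient and on the low cost of correction.

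The conclusion rests on Protocol Version 4. The synopsis in the SAP is from Version 5, whose Section 4.6 was not available, so whether the wording has since changed cannot be determined.

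**What to change.** Reconcile 4.6.1, 4.6.3, Table 4 and 5.4.3.1 so that a life-threatening infusion reaction and ongoing pregnancy each carry one consistent instruction wherever they appear. A condition may stay on both the pre-dose list and the discontinuation list, provided that the instruction is the same in both. If 4.6.1 keeps its two options, it should state which applies to each condition. Add a reference to 4.6.3 in 4.6.1 and in footnote k of Appendices 1, 2 and 3. The sponsor's clinical team must decide which rule applies, and none is proposed here.

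Check the latest protocol version first. If the wording is still there, the cost is a text change carried through the amendment process in Protocol 9.6. Sample size, endpoints and the SAP's analyses are unaffected.

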4.6.2 Patient Discontinuation

Patients have the right to voluntarily withdraw from the study at any time for any reason. In addition, the investigator has the right to withdraw a patient from the study at any time. Reasons for withdrawal from the study may include, but are not limited to, the following:

- Patient withdrawal of consent at any time
- Any medical condition that the investigator or Sponsor determines may jeopardize the patient's safety if he or she continues in the study
- Investigator or Sponsor determines it is in the best interest of the patient
- Patient non-compliance, defined as failure to follow dosing instructions or to complete program visits

Every effort should be made to obtain information on patients who withdraw from the study. The primary reason for withdrawal from the study should be documented on the appropriate eCRF. However, patients will not be followed for any reason after consent has been withdrawn. Patients who withdraw from the study will not be replaced.

4.6.3 Study Treatment Discontinuation

Patients must discontinue study treatment if they experience any of the following:

- Ongoing pregnancy: Please note that the pregnancy should be followed up to determine outcome, including spontaneous or voluntary termination, details of birth, and the presence or absence of any birth defects, congenital abnormalities, or maternal and newborn complications.
- Life-threatening IRR or serious hypersensitivity reaction
- Active hepatitis B infection or reactivation
- PML
- Active tuberculosis, either new onset or reactivation

The primary reason for study treatment discontinuation should be documented on the appropriate eCRF. Patients who discontinue study treatment prematurely will not be replaced.

4.6.4 Study and Site Discontinuation

The Sponsor has the right to terminate this study at any time. Reasons for terminating the study may include, but are not limited to, the following:

- The incidence or severity of adverse events in this or other studies indicates a potential health hazard to patients.
- Patient enrollment is unsatisfactory.

The Sponsor will notify the investigator if the Sponsor decides to discontinue the study.

The Sponsor has the right to close a site at any time. Reasons for closing a site may include, but are not limited to, the following:

- Excessively slow recruitment
- Poor protocol adherence
- Inaccurate or incomplete data recording
- Non-compliance with the International Council on Harmonisation (ICH) guideline for Good Clinical Practice
- No study activity (i.e., all patients have completed the study and all obligations have been fulfilled)

5. ASSESSMENT OF SAFETY

5.1 SAFETY PLAN

Ocrelizumab is currently in clinical development for the treatment of MS. Identified and potential risks associated with ocrelizumab treatment will continue to be closely monitored throughout the clinical program. Patient safety during the ocrelizumab program is ensured by targeting the most appropriate patient population, stringent safety

monitoring by the Sponsor, and protocol-specified ocrelizumab treatment interruption criteria. Patients will be evaluated clinically and with standard laboratory tests before the study and at regular intervals during the study. Safety evaluations will consist of medical interviews, recording of adverse events, physical examinations, and standard laboratory measurements. Adverse events will be graded according to National Cancer Institute Common Terminology Criteria for Adverse Events, Version 4.0 (NCI CTCAE v4.0).

Administration of ocrelizumab will be performed in a hospital or clinic environment under close supervision of the investigator or a medically qualified staff member with immediate availability of full resuscitation facilities. All adverse events and serious adverse events will be recorded during the study and for up to 48 weeks after the last dose of ocrelizumab as provided through this study. Related serious adverse events must be collected and reported regardless of the time elapsed from the last study drug administration, even if the study has been closed. If the patient is unable to return for the safety follow-up visit, the discontinuation visit information may be collected via phone call.

Safety assessments will include the incidence, nature, and severity of (serious) adverse events graded per the NCI CTCAE v4.0. Safety assessments will be conducted *for the RMS cohort Arms 1–3 per the schedule of activities in Appendix 1, for the RMS cohort Arm 4 per the schedule of activities in Appendix 2, and for the PPMS cohort per the schedule of activities in Appendix 3.*

The potential safety issues anticipated in this study, as well as measures intended to avoid or minimize these issues, are outlined in the following sections.

5.1.1 Risks Associated with Ocrelizumab

5.1.1.1 *Identified Risks and Adverse Drug Reactions*

5.1.1.1.1 *Infusion-Related Reactions*

All CD20-depleting agents administered via the intravenous route, including ocrelizumab, have been associated with acute IRRs. Symptoms of IRRs may occur during any ocrelizumab infusion, but have been more frequently reported during the first infusion. Physicians should alert patients that IRRs can occur within 24 hours of the infusion. These reactions may present as pruritus, rash, urticaria, erythema, throat irritation, oropharyngeal pain, dyspnoea, pharyngeal or laryngeal edema, flushing, hypotension, pyrexia, fatigue, headache, dizziness, nausea, and tachycardia.

Patients should be observed for at least one hour after the completion of the infusion for any symptom of IRR. They will be informed about the possibility of delayed post-infusion symptoms and instructed to contact their study physician if they develop such symptoms.

Hypotension, as a symptom of IRR, may occur during ocrelizumab infusions. Therefore, withholding of antihypertensive treatments should be considered for 12 hours prior to and throughout each ocrelizumab infusion.

5.1.1.2 Infections

Infection is an identified risk associated with ocrelizumab treatment, predominantly involving mild to moderate respiratory tract infections. Non-disseminated herpes virus-associated infections, mostly mild to moderate, were also reported more frequently with ocrelizumab (approximately 5% to 6%, simplex and zoster) than with comparators (approximately 3%).

During the controlled period of the pivotal trials, the proportion of patients with serious infections was lower in RMS in the ocrelizumab group (1.3%) than in the interferon beta-1a group (2.9%); in PPMS, the proportion of patients with serious infections was similar in both groups: 6.7% in the placebo group compared with 6.2% in the ocrelizumab group.

Serious, opportunistic, and fatal infections have occurred in patients with lupus and rheumatoid arthritis (RA) treated with ocrelizumab in Phase III clinical trials. Data from completed studies regarding infection risks with ocrelizumab treatment in these patient populations are provided in the Ocrelizumab Investigator's Brochure.

No opportunistic infections were reported by any MS patient treated with ocrelizumab.

There were no reports of hepatitis B reactivation in MS patients treated with ocrelizumab, but it had been reported in one RA patient treated with ocrelizumab. HBV screening should be performed in all patients before initiation of treatment with ocrelizumab as per local guidelines. Patients with active hepatitis B virus should not be treated with ocrelizumab. Patients with positive serology should consult liver disease experts before the start of treatment and should be monitored and managed following local medical standards to prevent hepatitis B reactivation.

There were no reports of PML in patients treated with ocrelizumab. JCV infection resulting in PML has been observed in patients treated with anti-CD20 antibodies and other MS therapies and associated with risk factors (e.g., patient population, polytherapy with immunosuppressants). However, a risk of PML cannot be ruled out. Healthcare professionals should be alerted to the early signs and symptoms of PML, which can include any new onset or worsening of neurological signs or symptoms as these can be similar to an MS relapse. Please refer to [Appendix 6](#) for guidance for diagnosis of PML.

Delay ocrelizumab administration in patients with an active infection until the infection is resolved.

